9.2 Assessments of outcomes

Participants will be seen in a healthcare facility in each center four times, at baseline, after 6-, 12- and 24- months. Data will be collected by study nurses, supervised by the responsible investigator at each site, based on protocols standardized across sites. All data will be directly collected via centralized computerized data entry forms. Laboratory analyses of urine samples will be centralized at the laboratory in Lausanne (Unisanté, Centre universitaire de médecine générale et santé publique, Lausanne). The laboratory is accredited ISO 17025 for nicotine quantification in urine, VOCs quantification, and it will use validated methods for the other compounds in urine and oxidative stress analyses. The samples are only stored and continued to be used with the participants consent independent from the study (see section 12.6). The blood samples from which analysis of blood lipids, HbA1c (only for participants with diabetes), creatinine will be performed, will remain in the main laboratory of each health center. The other blood sample for the analyses of inflammatory biomarkers from the centers in St. Gallen and Bern will be transported and stored in the biobank in Bern. Blood samples from participants in Geneva are stored at the local biobank in Geneva. Analyses of exhaled breath condensates will only be performed in Lausanne and thus centralized at the laboratory in Lausanne (Unisanté, Centre universitaire de médecine générale et santé publique, Lausanne). CTU Bern personnel will monitor quality. We will inform participants that some random phone calls will be recorded for quality monitoring. Quality monitoring will include reviewing calibration procedures for carbon monoxide (CO) and blood pressure measuring devices, weight and height scales.

The table below shows which outcome markers listed in 9.1 are collected in which center:

Tobacco use (questionnaires)	Bern, Geneva, Lausanne, St. Gallen, Zürich
Estimated ENDS use (ml e-liquids used)	Bern, Geneva, Lausanne, St. Gallen, Zürich
Exhaled CO	Bern, Geneva, Lausanne, St. Gallen, Zürich
Urinary nicotine, cotinine, anabasine	Bern, Geneva, Lausanne, St. Gallen, Zürich

Urinary metabolites of nitrosamines (TSNAs)	Bern, Geneva, Lausanne, St. Gallen, Zürich
Adverse events, serious adverse events	Bern, Geneva, Lausanne, St. Gallen, Zürich
VOC and PAH metabolites in urine	Bern, Geneva, Lausanne, St. Gallen, Zürich
Oxidative stress markers in urine	Bern, Geneva, Lausanne, St. Gallen, Zürich
Oxidative stress in exhaled breath (Lausanne site only)	Lausanne
Blood pressure, heart rate, height, weight (BMI), waist circumference	Bern, Geneva, Lausanne, St. Gallen, Zürich
Blood lipids, HbA1c (only for participants with diabetes), creatinine	Bern, Geneva, Lausanne, St. Gallen
Respiratory symptoms	Bern, Geneva, Lausanne, St. Gallen, Zürich
Pulmonary function test parameters (FEV1, FVC, FEV1/FVC, PEF, FEF25-75%, TLC, FRC, RV/TLC, DLCO) (Bern site only)	Bern (150 participants)
Multiple breath washout (MBW) parameters (LCI, Scond, Sacin) (Bern site only)	Bern (150 participants)
Parameters of ventilation, perfusion and structural changes of the lung (MRI; Bern site only)	Bern (40 participants & 10 healthy volunteers)
Micronuclei frequency (micronuclei assessment)	Bern, Lausanne
Olfactory function parameters ((olfactory discrimination score (ODS))	Bern, Geneva, Lausanne, St. Gallen, Zürich
"Dry-hit" recognition	Bern, Geneva, Lausanne, St. Gallen, Zürich
Inflammatory biomarkers	Bern, Geneva, St. Gallen

9.2.1 Assessment of primary outcome

- The primary outcome at 6-month will be the continuous smoking abstinence from target quit date to the 6-month follow-up visit, ascertained by self-report at the 6-months visit (self-report of no smoking from target quit date) and confirmed by urinary level of anabasine (<3 ng/ml). Complete Urine samples will be collected in a flask. The laboratory in Lausanne (Unisanté, Centre universitaire de médecine générale et santé publique, Lausanne) has a routine analytical method for measuring nicotine metabolites in urine and participates regularly in external quality control testing.
- The primary outcome at 12- and 24- months follow-up will be the self-reported 7-day point prevalence abstinence (not having smoked cigarettes within the preceding week), confirmed by urinary level of anabasine (<3 ng/ml).

9.2.2 Assessment of secondary outcomes

The secondary outcomes will be measured as described for the primary endpoint.

Secondary smoking cessation outcome will be measured with a self-reported 7-day point prevalence abstinence (not having smoked cigarettes within the preceding week), again confirmed by urinary level of anabasine, and change in the self-reported number of cigarettes smoked per day (CPD) with 50% reduction in CPD from baseline to follow-up considered as successful reduction, measured as above.

For alternate validation methods of the primary and secondary outcomes, we will use CO-levels, which will be measured with a Micro Smokerlyser®; Bedfont Scientific Ltd.

Respiratory symptoms will be assessed by questionnaires:

- COPD Assessment Test (CAT), Modified Medical Research Council (MMRC) Scale, Asthma Test (ACT/ ECRHS)

Each Urine sample will be split into six aliquots to quantify cotinine and anabasine (see above), PAH metabolites, VOCs, propylene glycol, TSNAs, 8-OHdG and 8-isoprostanes, since no analytical method can measure all the compounds together. The different compounds will be estimated as follows:

- Concentrations of urinary cotinine and anabasine, VOCs, TSNAs and PAHs will be measured
- Oxidative stress will be assessed by quantifying 8-OHdG and 8-isoprostane concentrations in both EBC and urine
- We will adapt the method for analyzing urinary TSNAs from Xia et al.³⁰ After enzymatic hydrolysis with a β -glucuronidase solution, the urine sample will be extracted using solid phase extraction (SPE) columns, and analyzed by LC/MS/MS.
- We will use a high performance liquid chromatography (HPLC) method developed by the IST laboratory to analyze PAHs (1- and 2-Naphthol and urinary 1-OHP).

Exhaled breath condensates (EBC) other than CO will be performed in all participants at the Lausanne site during the first as well as the outcome visit (baseline and 6 months), based on guidelines from the American Thoracic Society (ATS)/European Respiratory Society (ERS) Task Force for EBC collection⁸⁷. EBC will be sampled with an EcoScreen II system (total exhaled volume of about 120 L). After collection, each sample will be aliquoted. To avoid auto-oxidation of fatty acids (potential impact on 8-isoprostane levels), we will add tert-butyl hydroxytoluene and rapidly freeze the sample. The samples will be stored at -70°C for a maximum of 1 month.⁹⁰

OHdG and 8-isoprostane will be simultaneously determined in EBC, using a method adapted to Syslova et al.⁹⁰ After adding internal standards (isotopically labeled 8-OHdG and 8 isoprostane), 1 ml of EBC will be lyophilized and the residue dissolved in a water:methanol solution and immediately analyzed by a liquid chromatography–atmospheric pressure ionization tandem mass spectrometry (LC-ESI-MS/MS) method available at IST.

Cardiovascular risk factors (CVRF) will be assessed as follows:

- Blood collection: We will measure cardiovascular risk factors in blood by routine methods in clinical practice: Total-, LDL- and HDL-cholesterol, triglycerides, HbA1c (only for participants with diabetes) and creatinine.
- Blood pressure and heart rate will be measured by standard sphygmomanometer. After a 10-minute rest, the right arm blood pressure of a seated participant will be assessed three times at one-minute intervals. The two last blood pressures measures will be averaged to reduce variability.
- Height, weight (calculation of body mass index, BMI), and abdominal circumference

.We will query all participants if they had SARS-CoV-2 testing during the outbreak.

Pulmonary function will be assessed in a subgroup of 150 participants at the Bern site using conventional pulmonary function tests and by multiple breath washout. Pulmonary function test results will be interpreted according to the current ERS/ATS guidelines¹⁵¹ and in the case of evidence for COPD according to the current GOLD report¹⁵². MBW results will be analyzed according to the current ERS/ATS consensus statement⁷⁷.

MRI and additional pulmonary function testing will be done in a subsample of at least 40 participants at the 6-month follow-up at the Bern site to assess functional and structural changes in the lung. Participants of both groups, (randomized participants who switched to vaping, who continued smoking and quitters of both smoking and vaping) will be invited to perform a MRI measurement and lung function measurement before and after vaping/smoking. Participants will be asked not to vape/smoke 3 hours prior to the first pulmonary function and MRI measurements. The participants will then be asked to vape/smoke (unless they've quit smoking/vaping) and the second pulmonary function and the MRI measurement will be performed less than 30 minutes after vaping/smoking. MRI is a non-invasive and radiation free diagnostic test used in clinical setting in children and adults. MRI provides images of different layers from the body. Measurements with a new developed implication for the MRI called the matrix pencil method (MP-MRI) will be performed. The method of MP-MRI allows simultaneous assessment of regional lung perfusion and ventilation in humans. For this technique, neither administration of intravenous contrast agents nor inhalative gaseous media is needed. Beside functional changes structural changes of the lung parenchyma will be examined. The MRI exams will be performed on a standard clinical whole body MRI with 1.5 Tesla field strength (MAGNETOM Avanto, Siemens Healthcare at the university hospital Basel; MAGNETOM Aera, Siemens Healthcare at the university hospital Bern). Participants coming on both days for the pulmonary function testing and MRI will be reimbursed with 90 CHF. To compare stability over a brief period of time (2 hours) of MRI outcome

measures, we will include a group of healthy volunteers (N=10) who will undergo two consecutive MRI measurements. Healthy volunteers will be never smokers/non-vapers (<100 cigarettes per lifetime), no history of lung disease, no use of inhalation medication and no lung infection in the last four weeks. Volunteers will be aged matched to our sub-group of participants of former smokers, tobacco smokers and participants using ENDS products. Most studies define a never-smoker as one who either has never smoked at all or has smoked <100 cigarettes (or the equivalent amount of tobacco) in his or her lifetime, which is in line with that proposed by the World Health Organization.¹⁵³

Micronuclei assessment in buccal epithelium, a surrogate measure of future cancer risk, will be done at baseline, and at the 6-, 12- and 24-months follow-up visits. Buccal cells will be harvested with a cytobrush. Participants will harvest their own cells by rotating the cytobrush on the inner cheeks of the mouth. The cytobrushes will be transferred or mailed to the laboratory in a buffer. The buccal cells will then be centrifuged, separated mechanically with tissue homogenizer, filtered, transferred onto microscope slides and left to air dry. The cells will be fixed in ethanol/glacial acetic acid and stained with DAPI (4',6-diamidino-2-phenylindole). An automatic MN counting system will be applied. MN frequency will be calculated as number of cells that contain MNs divided by the total number counted. A minimum of 1000 cells will be counted per participant.

The olfactory function will be assessed at baseline and at the 6-, 12- and 24-months follow-up visits by using the Burghart Sniffin' Sticks 16-item Identification-test.^{110-112, 154} The participants will be asked to not have eaten, drunk anything but water, smoked, used ENDS or chewed gum for at least 15 minutes before the olfactory function test. 16 commonly known odours will be presented to the participants for around 3-4s each, after which the participants will be asked to select the correct answer from 4 possible answers (forced choice). The highest possible score olfactory identification score (OIS) is 16; the cut-off for hyposmia is 11 points and cut-off for anosmia is 8 points. This will be performed at baseline and at the 6-, 12- and 24-months follow-up visits.

For the "dry-hit" recognition, voluntary participants will be given two ENDS at the 6 months follow-up visit – one with correct filling of the e-liquid and one with a too low e-liquid level and therefore producing a "dry hit" which would be recognized as a burnt smell when vaping. They are asked to assess which one is the ENDS producing a "dry-hit". Both ENDS will be filled with a tobacco flavored e-liquid without nicotine (0mg/ml). The participants will be instructed to take at least 1 puff of 2 seconds (maximum of 4 puffs of 2 seconds each with a 30 second break in-between) from each ENDS. Participants will not be informed about the sequence of the ENDS. Participants are allowed to go back and forth between the two ENDS before they decide. After their decision, they will be informed, if they were able to recognize the ENDS which generates a "dry hit". The inflammatory biomarkers will be measured in blood serum using Olink Proteomics' unique protein detection system,¹¹⁸ the Proximity Extension Assay (PEA), which allows us to perform highly specific and sensitive multiplex immunoassays to detect 92 inflammation-related protein biomarkers.

Several questionnaires will be used to assess further parameters:

- Demographics: Age, gender; Socio-economic: education level, marital status; medical history, including medication use and healthcare utilization.
- Smoking history,^{155, 156} including Fagerström questionnaire to assess nicotine dependence¹⁵⁷ and the Minnesota nicotine withdrawal scale.¹⁵⁸
- Physical activity (International Physical Activity Questionnaire, IPAQ)¹³⁸
- legal and illegal drug use: Alcohol consumption (AUDIT-C)^{141, 159}, illegal drug use (cannabis, cocaine, other)¹⁴²
- Quality of life (EQ-5D questionnaire)¹⁴⁴
- Depression symptoms (PHQ-9)¹⁶⁰
- Anxiety (GAD-7)¹⁴⁶
- Sleep Quality (PSQI)¹⁴³
- Environmental pollution exposure (e.g. second hand smoke)^{147, 148}

9.2.3 Assessment of other outcomes of interest

See above.

9.2.4 Assessment of safety outcomes

Information on safety outcomes like Adverse Events and ENDS deficiencies will be collected proactively

during the phone calls and the 6-, 12- and 24- month follow-up visits in person visit using standardized questionnaires and international guidelines.¹⁴⁹

9.2.4.1 Adverse events

For this trial, all AEs as well as all SAEs will be collected, fully investigated, and documented in the source documents and the eCRF for all participants from the date of ICF signature until the last protocol-specific procedure has been completed.

9.2.4.2 Laboratory parameters

See above (assessment of secondary outcomes)

9.2.4.3 Vital signs

See above (assessment of secondary outcomes)

9.2.5 Assessments in participants who prematurely stop the study

Subjects who permanently discontinue study treatment are encouraged to continue in the follow-up period and to attend the protocol-specified follow-up visit at 6 months in accordance with the intention-to-treat principle.

9.3 Procedures at each visit

9.3.1 Screening phone call at -x to -8 days to target quit date:

- Study information and explanation
- Eligibility check (inclusion/exclusion criteria)
- Scheduling of target quit date and baseline visit
- Smoking history

9.3.2 Visit 1, Baseline visit at -7 days to target quit date

- Patient information and delivery of written study information to subject
- Verification of eligibility, including urine pregnancy test for premenopausal women
- Informed consent
- Demographics
- Relevant medical history including current medication
- Smoking history and symptoms linked to smoking, cigarette dependence (Fagerström Test for Cigarette Dependence), withdrawal symptoms
- Body weight, height, calculation of BMI, waist circumference
- Vital signs (heart rate, systolic and diastolic blood pressure at the right arm after at least 5 minutes at rest sitting)
- Questionnaires
 - Respiratory symptoms
 - Quality of life
 - Physical activity
 - Anxiety
 - Depression
 - Sleep quality
 - Alcohol and illegal drug use
 - Environmental pollution exposure
- Exhaled breath composition (CO, oxidative stress markers in a subset of participants)
- Blood collection (lipids, HbA1c (only for participants with diabetes) & creatinine, inflammatory biomarkers)
- Urine collection (nicotine metabolites, VOCs, PAHs, nitrosamines, oxidative stress markers)
- Randomization to study group
- Distribution and instruction of ENDS and e-liquids (intervention group only)
- Smoking cessation counselling

- Scheduling of phone calls
- Pulmonary function tests (conventional and MBW in a subset of participants)
- Micronuclei assessment in buccal epithelium
- Olfactory function: Burghart Sniffin' Sticks 16-Item Identification Test
- Inflammatory biomarkers
- .

9.3.3 Phone calls at target quit date, week 1, week 2, week 4, and week 8

Phone calls at target quit date (corresponding to day 0) and after 1 week (± 2 days), 2 weeks (± 3 days), 4 weeks (± 4 days), and 8 weeks (± 1 week):

- Smoking status: cigarettes / ENDS
- Assessment of smoking cessation medication use: NRT, proven effective drug therapies (varenicline, bupropion) and other interventions without demonstrated efficacy (e.g. acupuncture, hypnose, sophrology etc)
- Assessment of AEs, ENDS deficiencies
- Smoking cessation counselling
- ENDS technical trouble shooting
- Scheduling of phone calls and outcome visit

9.3.4 Outcome visit (month 6)

Visit at 6 months (corresponding to 24 weeks (-4 weeks/+12 weeks) after the target quit date):

- Current medication
- Antibiotics within the last 6 months
- Smoking status, nicotine dependence (Fagerström questionnaire), withdrawal symptoms
- Assessment of AEs, ENDS deficiencies Body weight, height, calculation of BMI, waist circumference
- Vital signs (heart rate, systolic and diastolic blood pressure at the right arm after at least 5 minutes at rest)
- Questionnaires
 - Respiratory symptoms
 - Quality of life
 - Physical activity
 - Anxiety
 - Depression
 - Sleep quality
 - Alcohol and illicit drug use
 - Environmental pollution exposure
-
- Exhaled breath composition (CO, oxidative stress markers in a subset of participants)
- Blood collection (lipids, HbA1c (only for diabetic participants) & creatinine, inflammatory biomarkers)
- Urine collection (nicotine metabolites, VOCs, PAHs, nitrosamines, oxidative stress markers)
- Pulmonary function tests (conventional and MBW in a subset of participants)
- MRI (in a subset of participants)
- Micronuclei assessment in buccal epithelium
- Olfactory function: olfactory identification score (OIS)
- "Dry-hit" recognition
-

9.3.5 Outcome visit (month 12)

Visit at 12 months (corresponding to 48 weeks after the target quit date):

- Current medication
- Antibiotics within the last 6 months
- Smoking status, nicotine dependence (Fagerström questionnaire), withdrawal symptoms
- Assessment of AEs, ENDS deficiencies
- Body weight, height, calculation of BMI, waist circumference
- Vital signs (heart rate, systolic and diastolic blood pressure at the right arm after at least 5 minutes at rest)

- Questionnaires
 - Respiratory symptoms
 - Quality of life
 - Physical activity
 - Anxiety
 - Depression
 - Sleep quality
 - Alcohol and illicit drug use
 - Environmental pollution exposure
- Blood collection (lipids, HbA1c (only for participants with diabetes) & creatinine)
- Urine collection (nicotine metabolites, VOCs, PAHs, nitrosamines, oxidative stress markers)
- Pulmonary function tests (conventional and MBW in a subset of participants)
- Micronuclei assessment in buccal epithelium
- "Dry-hit" recognition
- Olfactory function: Burghart Sniffin'Sticks 16-Item Identification Test

9.3.6 Outcome visit (month 24)

Visit at 24 months (corresponding to 96 weeks after the target quit date):

- Current medication
- Antibiotics within the last 6 months
- Smoking status, nicotine dependence (Fagerström questionnaire), withdrawal symptoms
- Assessment of AEs, ENDS deficiencies
- Body weight, height, calculation of BMI, waist circumference
- Vital signs (heart rate, systolic and diastolic blood pressure at the right arm after at least 5 minutes at rest)
- Questionnaires
 - Respiratory symptoms
 - Quality of life
 - Physical activity
 - Anxiety
 - Depression
 - Sleep quality
 - Alcohol and illicit drug use
 - Environmental pollution exposure
- Blood collection (lipids, HbA1c (only for participants with diabetes) & creatinine)
- Urine collection (nicotine metabolites, VOCs, PAHs, nitrosamines, oxidative stress markers)
- Pulmonary function tests (conventional and MBW in a subset of participants)
- Micronuclei assessment in buccal epithelium
- "Dry-hit" recognition
- Olfactory function: Burghart Sniffin'Sticks 16-Item Identification Test

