Effect of ENDS on SARS-CoV2 infection and COVID-19-associated SAEs

By April 2020, the COVID-19 pandemic raged worldwide. Europe is now an active site with a steeply increasing rate of deaths from the disease as it spreads through the population. SARS-CoV-2 is a positive-sense RNA coronavirus that can cause severe acute respiratory syndrome (COVID-19),⁶⁵ and is especially dangerous to older patients with comorbid conditions. Mortality is higher in men than women.^{66, 67} Since men are more likely to be smokers than women, tobacco smoking might contribute to the higher risk of mortality in men. This is the case for influenza: hospitalized smokers likelier to have poor outcomes.⁶⁸ It is unclear if tobacco smoking poses an independent risk or if poorer outcomes result from underlying health conditions caused by long-term tobacco smoking. Tobacco smoking has an immunosuppressive effect,⁶⁹ and there may also be a biological explanation for increased SARS-CoV-2 infection among smokers.^{70, 71} But we can only verify these suppositions by studying the effects of SARS-CoV-2 among smokers of tobacco cigarettes and comparing outcomes with those who use electronic nicotine delivery systems (ENDS) that do not produce tobacco smoke (vaping). Whilst recent randomised controlled trials (RCT) suggest ENDS effectively help smokers quit, the largest RCT to date found a worrisome, albeit not statistically significant increase in rate of hospitalisation for infection-related diseases in participants allocated to ENDS use.¹² Experiments conducted in the lab suggest ENDS vapour, like traditional cigarette smoke, might lead to immunosuppression.^{72, 73} We have no data on the association between ENDS use and SARS-CoV-2 infection rates. In addition to scheduled outcomes collected in the trial, we will query all participants about symptoms of infection, SAEs, and any antibiotic prescriptions.

Effect of ENDS on lung function and MBW

One study compared the short term effects of cigarette smoking compared to ENDS smoking and found that cigarette smoking led to a higher acute reduction in FEV1/FVC compared to ENDS.⁶¹ Short term airway resistance has been studied in various small, short term studies, with conflicting results.^{62, 63} This

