10.4.1 Definition and assessment of (serious) adverse events

An **AE** is any untoward medical occurrence in participant administered an intervention a clinical investigation and which does not necessarily have a causal relationship with the intervention. An AE can therefore be any unfavourable and unintended sign (including an abnormal laboratory finding), symptom, or disease temporally associated with the intervention, whether or not related to the intervention. [ICH E6 1.2, adapted]

A **SAE** is classified as any event which:

- requires inpatient treatment of at least 24 hours or extends a current hospital stay;
- results in permanent or significant incapacity or disability;
- is life-threatening or results in death; or
- causes a congenital anomaly or birth defect.

In addition, important medical events that may not be immediately life-threatening or result in death, or require hospitalisation (regardless of the duration of the hospitalization), but may jeopardise the patient or may require intervention to prevent one of the other outcomes listed above should also usually be considered serious.

A hospitalisation or a prolongation of a current hospitalisation for a diagnostic or elective (surgical) procedure that was already planned prior to the participant's enrolment into the study is not classified as an SAE.

SAEs should be followed until resolution or stabilisation. Participants with ongoing SAEs at study termination will be further followed up until recovery or until stabilisation of the disease after termination, or until the participant is lost to follow-up.

Assessment of Causality

The assessment of causality of SAEs will be done by both, investigator and Sponsor based on the criteria listed in the ICH E2A guidelines below. For events of special interest (all SAEs, respiratory events, cardiovascular events, AEs with prescription of systemic antibiotics and AEs for which a causal relationship between the AE and vaping or smoking is not excluded) a smoking assessment questionnaire will be filled out in relationship to the event to facilitate the assessment of causality.

Relationship	Description
Definitely	Temporal relationship Improvement after dechallenge* Recurrence after rechallenge (or other proof of drug cause)
Probably	Temporal relationship Improvement after dechallenge No other cause evident
Possibly	Temporal relationship Other cause possible
Unlikely	Any assessable reaction that does not fulfil the above conditions

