June 21 st , 2018	Approval of changes: 
 1. Change from principal-investigator (PI) to sponsor and coordinating person 	Protocol version 4.0, Dated June 12 th , 2018. Administrative change of role of [name]. med [name] from Sponsor-investigator to Sponsor and coordinating person.
August 21 st , 2018	Approval of study site Geneva	Protocol version 4.0, Dated June 12 th , 2018. Study site Geneva allowed to recruit in addition to study site Bern.
December 18 th , 2018	Approval of study site Lausanne Approval of changes: 
 1. Primary outcome specified 2. Change of PI at study site in Lausanne 3. Addition of e-liquid nicotine concentration: 0mg/ml 	Protocol version 5.0, Dated October 30 th , 2018. Study site Lausanne allowed to recruit in addition to study site Bern and Geneva. Primary outcome validation was changed from CO level and urinary level of cotinine, anabasine and NNAL to urinary level of anabasine and CO for consistency.
June 27 th , 2019	Approval of changes: 
 1. Addition of "Apple" aroma 2. Systematic questions on antibiotics prescriptions and reasons for prescriptions 3. Adding preference scale 	Protocol version 6.0, Dated May 9 th , 2019. 
 1. During consultations, some participants asked for "Apple" aroma in addition to the other aromas provided. We added this aroma to ensure adherence to the e-liquids provided by the study nurses. 2. The publication of a large trial testing efficacy of ENDS for smoking cessation suggested a trend towards more respiratory infections. We added a question at follow-up visits to further detect AE related to respiratory infections.

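### At the 24-month visit the antibiotic item looks back 6 months over a 12-month interval, so no antibiotic question covers roughly months 12 to 18

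*Supplement*

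**What the plan says.** Protocol 9.0 lists the item "Antibiotics within the last 6 months" in identical words at the month-6, month-12 and month-24 visits (9.3.4, 9.3.5, 9.3.6). The schedule in 9.1 places these visits at days 180, 360 and 720 after the target quit date, each with a window of −4/+12 weeks. After the week-8 call these three visits are the only contacts.

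The protocol gives two statements of purpose. Section 3.1, in the part on SARS-CoV-2, notes a worrisome but non-significant excess of infection-related hospitalisation under ENDS in the largest earlier trial, and then says that "we will query all participants about symptoms of infection, SAEs, and any antibiotic prescriptions". No look-back is attached. The history of changes, under version 6.0, explains the item itself: "We added a question at follow-up visits to further detect AE related to respiratory infections".

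General safety collection runs alongside. Section 9.2.4.1 collects all AEs and SAEs "from the date of ICF signature until the last protocol-specific procedure has been completed", and 9.2.4 has them asked about "during the phone calls and the 6-, 12- and 24- month follow-up visits in person visit using standardized questionnaires". Section 10.4.1 counts "AEs with prescription of systemic antibiotics" among the events of special interest, for which a smoking assessment questionnaire is filled in.

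**The concern.** A 6-month recall suits a visit that follows the previous one by 6 months. It does not suit month 24, which follows by 12. A nurse working from 9.3.6 asks about months 18 to 24 only, and an antibiotic course in months 12 to 18 lies outside the question.

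The sequence of amendments suggests a carry-over. The antibiotic question came with version 6.0, when month 6 was the only follow-up visit. Version 7.0 then extended follow-up to 12 and 24 months. No reason is given for asking about only half of the second year.

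At stake is how well the trial detects antibiotic-treated infections in the extended follow-up, a safety question that the protocol itself raises. A course that is not elicited may also mean that the event is not recognised as one of special interest, so that its smoking assessment questionnaire is not completed.

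**Working it through.** The plan states no figure for this coverage, so there is none to reproduce. The check is interval arithmetic.

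**Inputs**
- Look-back L: 6 months, taken as 182 days (assumption; 180 and 183 also tried).
- Month-12 visit D12: day 360, window 360 − 28 = 332 to 360 + 84 = 444 (section 9.1).
- Month-24 visit D24: day 720, window 720 − 28 = 692 to 720 + 84 = 804 (section 9.1).
- Sections 9.3.5 and 9.3.6 give the same visits in weeks: 48 and 96 weeks after the target quit date.

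**Formula.** Days under no antibiotic item: G = (D24 − L) − D12.

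**Results from the schedule in 9.1**

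| Visit dates | L = 182 | L = 180 | L = 183 |
|---|---|---|---|
| Nominal (360, 720) | 720 − 182 − 360 = 178 | 180 | 177 |
| Late month 12, early month 24 (444, 692) | 692 − 182 − 444 = 66 | 68 | 65 |
| Early month 12, late month 24 (332, 804) | 804 − 182 − 332 = 290 | 292 | 289 |

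At nominal timing the month-24 item covers days 538 to 720 and leaves days 360 to 538, which is 178/360 = 49% of the interval between the two visits. G stays positive at the most favourable corner, so no permitted pair of dates closes the gap.

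**Results from the week-based text.** 96 − 26 − 48 = 22 weeks uncovered. If the windows of 9.1 are applied to these dates, the shortest interval is (672 − 28) − (336 + 84) = 224 days, still 224 − 182 = 42 days longer than the look-back.

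**Comparison with months 6 to 12.** Nominally 360 − 182 − 180 = −2, so there is no gap. With an early month-6 visit (day 152) and a late month-12 visit (day 444) it is 444 − 182 − 152 = 110 days. A fixed period can therefore miss time there too, but only off the nominal dates.

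**What else covers days 360 to 538.** AE and SAE collection is continuous, and the month-24 list in 9.3.6 includes an AE assessment. The period is thus asked about in general terms, by recall of up to a year or more, but without the antibiotic prompt.

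**The case against.** The strongest reply is that only a supplementary prompt lapses. All AEs and SAEs are recorded from consent onwards and asked about actively at month 24. The signal cited in 3.1 is hospitalisation for infection. An inpatient stay of at least 24 hours is an SAE under 10.4.1, and all SAEs go to adjudication, so its capture does not depend on this item. Version 7.0, which added the later visits, also strengthened AE documentation through systematic queries to hospitals and treating physicians. A 6-month recall matches the healthcare-use items in the SAP baseline table and limits recall error. All of this stands, and it limits the consequence. It does not explain why the prompt should stop halfway through the interval, nor does it square the item with the unlimited undertaking in 3.1.

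Several stronger readings are tempting, but the documents do not support them:
- *The infection signal goes uncovered in months 12 to 18.* General AE and SAE collection covers that period.
- *A quarter of antibiotic courses is lost*, from 178/720 = 25%. This needs a constant rate and no capture outside the item. The documents give no capture rate, and AE questioning will catch some courses.
- *Courses are counted twice when visits fall close together.* A month-6 visit on day 264 and a month-12 visit on day 332 do overlap, by 264 − (332 − 182) = 114 days. But neither section 11 of the protocol nor the SAP counts courses, and nothing shows that visit timing differs between arms.
- *The gap removes a whole winter.* That depends on the month of the quit date and on an assumed seasonality. For other quit dates the second winter lies within months 18 to 24.

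**Conclusion.** The point holds as a mismatch between a look-back and a visit interval. No antibiotic question covers roughly months 12 to 18: about 178 days at the scheduled dates and about 65 to 290 days across the visit windows. Detection of antibiotic-treated infections in that period rests on general AE and SAE reporting alone.

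The gap follows from one schedule applied to both arms, so the main cost is sensitivity: fewer events found in each arm, and less chance of seeing a difference in year two. How much is lost cannot be stated from the documents. The 6-month primary analysis is not affected, and SAP 2.0 leaves the 12- and 24-month outcomes out of its scope (section 2.7 and Table 4).

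The figures assume that 6 months means 180 to 183 days, that the dates and windows in 9.1 apply, and that the question is put as 9.3.6 words it. The questionnaire itself is not among the documents. If it already asks about the time since the last visit, only the protocol wording needs correcting. This is a cheap improvement to safety detection, not a threat to the trial's main result.

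**What to change.** In 9.3.4, 9.3.5 and 9.3.6, and in the matching eCRF item, replace the fixed 6-month period with: *antibiotics since the last study visit (since baseline at month 6), with start date and reason*. This brings G to zero for every pair of visit dates that the windows allow. A fixed 12-month period at month 24 would close the nominal gap but not the longer ones. It also brings the item into line with section 3.1.

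The cost is one line in the protocol and one changed item with a date field. The downside is less exact recall over 12 months than over 6, which recording the start date limits. The change works only for month-24 visits still to come, because month 24 is the last scheduled contact. For participants already seen, the report should state that the antibiotic item covered only the last 6 months of the interval.
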